2.0 HYPOTHESES, BACKGROUND, AND INTRODUCTION

2.1 Hypotheses

2.1.1 Treatment with BtB will improve FMD, increase circulating EPC/ECFC levels, and reduce circulating levels of IL-6, hsCRP, D-dimer, and markers of monocyte activation (CD14+CD16+ cell proportions and sCD14/sCD163) at both 12 and 24 weeks when compared to UC.

2.1.2 Treatment with BtB will improve PHQ-9 and SCL-20 scores at both 12 and 24 weeks when compared to UC.

2.1.3 Treatment with BtB will be safely tolerated and have no effects on HIV-1 RNA suppression or CD4 cell counts.

2.1.4 Genetic variation is associated with endothelial function, depression severity, and response to depression treatment.

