If an enrolled participant reports having thoughts of being better off dead or of hurting him/herself during any telephone calls (e.g., a scheduling call or a call to the study team initiated by the participant), the exact same procedures as outlined above will immediately be initiated. Please see the Appendix for the full Suicide Management Plan.

Since it is unknown if depression therapy (or lack thereof) results in somatic adverse events in antiretroviral-treated HIV-infected patients, we will also carefully document Grade 3 or 4 level toxicities defined using the Division of AIDS Table for Grading Adult Adverse Experiences. Clinical management decisions and decisions to discontinue participants from the trial will be made by the principal investigator(s) in conjunction with the participant's primary caregiver; care plans and outcomes must be included in the source documentation. All serious adverse events (SAEs) will be documented on CRFs with unexpected SAEs forwarded to the IUPUI IRB within 10 working days of the event and the remainder to be documented on the annual continuing review.

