9.0 STATISTICAL CONSIDERATIONS AND DATA MANAGEMENT

9.1 General Considerations

Data management and statistical analyses will be the responsibility of the Department of Biostatistics at IUSM. Parameter estimates and relevant summary statistics will be reported for both efficacy and side effects. Continuous variables will be summarized by means, medians, minima, maxima, and standard deviations. Categorical variables will be summarized by frequencies and percentages. Additional exploratory analyses will be performed when appropriate. Normality of variables will be checked and, if violated, nonparametric methods will be adopted. Changes from the analysis plan will not require an amendment to the protocol unless it changes a significant feature of the study. All analyses will be performed using SAS 9.4 (SAS Inc., Cary, NC).

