9.5 Analysis Datasets

Datasets	Definition
Intention-to-treat (ITT)	This will comprise all patients who meet the eligibility criteria and are randomized onto the study irrespective of their compliance to the planned course of treatment.
Per Protocol Set	This will comprise all UC patients and BtB participants who finish at least 6 out of 8 sessions.
Safety	This will comprise the BtB patients that attend at least one session of treatment.

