9.7 Disposition

The number of enrolled subjects will be summarized in a flow chart with frequency of completion and discontinuation. The subjects discontinued from BtB and their corresponding information will be listed. Significant protocol violations will be tabulated and/or listed.

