9.11 Analysis Plan for Secondary Objectives

Both unadjusted comparisons and adjusted comparisons between UC and BtB will be performed for secondary outcomes defined in 1.2.1-1.2.3. For adjusted comparisons, multiple linear regression models will be constructed to include treatment group, baseline characteristics [demographics, SCL-20 scores, tobacco/exercise/adherence questionnaire results, ART drugs/regimens (including efavirenz (142-144)), antidepressant use, co-morbidities, CD4 cell counts, and HIV-1 RNA levels], and time-varying characteristics (changes in SCL-20 scores, questionnaire results, CD4 cell counts, ART drugs/regimens, HIV-1 RNA levels) to determine their effects on the outcomes. Pearson and Spearman correlation coefficients will be estimated for FMD, IL-6, hsCRP, D-dimer, circulating EPCs/ECFCs levels, and markers of monocyte activation (CD14+CD16+ cell proportions and sCD14/sCD163) with PHQ-9 and SCL-20 scores at baseline. These analyses will be performed for both the intent-to-treat set and the per-protocol set. Dose-response relationships between 12- and 24-week FMD and the number of BtB sessions, which have a range from 0 to 8, will be explored.

Safety assessments will be performed using the safety dataset. HIV-1 RNA levels and CD4 cell counts of the BtB arm during the trial will be summarized and compared to the UC arm.

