Drs. [name] and/or [name] will review all cases screening positive for suicidal ideation immediately to determine the appropriate course of action – e.g., interview the patient to obtain further information, immediately contact the patient’s HIV provider or clinical social worker to involve them in the decision-making process, consult with clinicians at the Eskenazi Health Midtown Community Mental Health Center to aid in the decision-making process, escort the patient to the Eskenazi Health Crisis Intervention Unit (‘warm handoff’), and/or contact the police if the patient is at imminent danger of harm and is refusing all care. Either [name] or [name] will also call the participant’s HIV provider notifying him/her of the situation if the provider was not involved in the decision-making process. Regardless of the exact course of action, the study team will ensure that the participant is connected to the appropriate existing clinical services. If the patient’s HIV provider no longer believes that the patient is appropriate for this trial following this situation, the patient will be withdrawn from the trial.

Of note, because patients exhibiting active suicidal ideation are not eligible for this trial, we expect that it will be a rare occurrence that an enrolled patient will screen positive for suicidal ideation. Zero enrolled participants in our two prior depression trials have exhibited suicidal ideation during their involvement in the studies.

(b) Study Telephone Contacts

If a participant reports having thoughts of being better off dead or of hurting him/herself (i.e., responds with a 1, 2, or 3 to PHQ-9 Item #9 or spontaneously reports suicidal ideation) during a study call (e.g., the start or end of a remote BtB session, a scheduling call, or a call to the study team initiated by the participant), the study coordinator or a graduate student research assistant will interview the participant to complete the Patient Suicidality Form (found below).

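### Adverse events and suicidal ideation are to be assessed for safety in the Beating the Blues arm only, although both arms record them; summarise them by arm

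*Combined protocol and SAP*

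**What the plan says.** Section 9.5 (Analysis Datasets) defines the safety set: "This will comprise the BtB patients that attend at least one session of treatment". Section 9.11 (Analysis Plan for Secondary Objectives) then applies it: "Safety assessments will be performed using the safety dataset". The next sentence of 9.11 gives the only safety contrast with UC: "HIV-1 RNA levels and CD4 cell counts of the BtB arm during the trial will be summarized and compared to the UC arm". The general between-arm comparisons in 9.11 are for objectives 1.2.1 to 1.2.3; safety is objective 1.2.5 and lies outside them.

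The safety hypothesis in section 2.1.3 reads: "Treatment with BtB will be safely tolerated and have no effects on HIV-1 RNA suppression or CD4 cell counts". Section 7.0 gives the reason for documenting Grade 3 and 4 toxicities: "Since it is unknown if depression therapy (or lack thereof) results in somatic adverse events in antiretroviral-treated HIV-infected patients".

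Two other places touch on safety reporting. Section 9.1 says "Parameter estimates and relevant summary statistics will be reported for both efficacy and side effects", naming no arm and no dataset. Section 10.6 has a panel review descriptions of all adverse events every six months, and states no comparison by arm.

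**The concern.** In adults with HIV and depression, serious illness and suicidal thoughts occur whether or not BtB is given. A count of events among BtB attenders alone cannot separate an effect of the program from that background. Nor can it inform the half of the section 7.0 question about going without therapy, since the participants who bear on that half are in UC.

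At stake is what can be said about tolerability. Section 2.4 presents this as the first test of BtB in an HIV-infected population, so its safety statement is likely to be carried forward. Under 9.5 and 9.11 that statement would rest on one-arm adverse-event summaries plus two HIV markers, with a randomized control arm available and unused.

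**Working it through.** **1. Is the comparator data collected?** The Schedule of Events (6.1) marks signs and symptoms, diagnoses and PHQ-9 at Weeks 12 and 24, and labels both visits as being for both groups. Section 6.2.5.6 puts signs and symptoms of every grade on the case report form. Section 7.0 documents Grade 3/4 toxicities, and serious adverse events on the case report form, without restriction by arm. The Appendix assesses ideation through PHQ-9 Item 9 at every main study visit. So events and Item 9 exist in both arms.

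**2. Does another section supply the contrast?** Sections 9.1 and 10.6 do not. PHQ-9 score is compared by arm at Weeks 12 and 24 under objective 1.2.3, and Item 9 contributes to that total. No analysis of Item 9 itself is stated, and a total can fall while Item 9 stays positive.

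**3. Denominators.** Section 9.3 gives 44 per arm evaluable and 55 per arm randomized. This reproduces: a two-sided t-test at 0.05 with 80% power and a standardized difference of 0.61 needs 43.17, rounded up to 44 per arm; 88 / (1 − 0.20) = 110. The safety set omits all of UC, 55 / 110 = 50%, plus any BtB participant who attends no session.

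**4. Number of ideation assessments.** Scheduled PHQ-9s after randomization: BtB 8 sessions + 2 visits = up to 10; UC 2 visits (3.4.1, 3.4.2, 6.1). An any-visit count would therefore be misleading. As an illustration, assume an independent probability q of a positive Item 9 at each assessment, the same in both arms. The chance of at least one positive is 1 − (1 − q)^k:

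| Assumed q | BtB, k = 10 | UC, k = 2 |
|---|---|---|
| 1% | 9.6% | 2.0% |
| 2% | 18.3% | 4.0% |
| 5% | 40.1% | 9.8% |

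The gap is purely one of ascertainment, so the between-arm summary should use Weeks 12 and 24 only.

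**5. Precision for ideation.** With no positive among n assessed, the exact (Clopper-Pearson) two-sided 95% upper limit is 1 − 0.025^(1/n). For n = 44 it is 8.0%; for n = 55 it is 6.5%.

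**6. Precision for Grade 3/4 events.** The documents give no rate, so equal counts per arm of 55 are assumed. The Newcombe interval takes the Wilson limits (l, u) for each arm; with equal proportions p its half-width is √[(p − l)² + (u − p)²].

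| Assumed count per arm | p | Half-width of the difference |
|---|---|---|
| 3 of 55 | 5.5% | ±10.1 points |
| 6 of 55 | 10.9% | ±12.4 points |
| 11 of 55 | 20.0% | ±15.0 points |

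For 11 of 55 the Wilson limits are 11.6% and 32.4%, and √(0.084² + 0.124²) = 0.150.

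**The case against.** The strongest defence is that the analysis matches its objective. Objectives 1.2.1 to 1.2.3 are worded as comparisons; 1.2.5 is worded as an assessment of BtB. Hypotheses 2.1.1 and 2.1.2 name UC as comparator; 2.1.3 does not. The section 7.0 phrase is a parenthesis in a sentence that commits only to documenting events. Section 9.1 also allows further exploratory analyses, so a by-arm table is not ruled out. All of this is fair, and it limits the seriousness. It does not supply the comparison: the one stated rule for safety assessments is BtB-only, and a table that is merely permitted may not appear.

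The trial is also a small single-center pilot, section 10.2.3 reports no known risks from the program, and the Appendix says "we expect that it will be a rare occurrence that an enrolled patient will screen positive for suicidal ideation". That argues for description with intervals and against a test. It does not argue for leaving out the control arm.

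Three stronger readings are tempting and should be resisted.

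- A reader might infer that UC participants with suicidal ideation are overlooked. They are not. Section 7.0 and the Appendix apply the same management to both arms; the gap is only in the planned summary.
- A reader might infer from section 9.7, "The subjects discontinued from BtB and their corresponding information will be listed", that UC withdrawals go unreported. That sentence most naturally means stopping the intervention, which a UC participant cannot do. The flow chart in 9.7 covers discontinuation for all enrolled subjects, and 10.6 requires immediate review of any discontinuation for an adverse event.
- A reader might infer that every ideation case found at a BtB session and resolved before Week 12 biases the later contrast towards BtB. Only a case that resolves because it was detected does so; one that would have resolved anyway has undetected counterparts in UC. The documents give no basis for putting a number on this.

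**Conclusion.** The point holds as a reporting gap. Sections 9.5 and 9.11 leave the tolerability conclusion without a concurrent comparator for adverse events or suicidal ideation, although both arms supply the data. The primary FMD inference is untouched.

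The gain from closing the gap is real but modest: a control-arm rate beside the BtB rate, with a 95% interval for the Grade 3/4 difference of about ±10 to ±15 points and an upper limit of 8.0% on a zero ideation count. These figures rest on 55 randomized and 44 assessed per arm (section 9.3) and, for Grade 3/4 events, on assumed rates of about 5% to 20%. Neither by-arm table could establish that the arms are equally safe. The change is a cheap improvement.

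**What to change.** In 9.5, define the safety set as all randomized participants, analysed by assigned arm. Keep BtB participants with at least one session as a supplementary set.

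In 9.11, add by-arm summaries, descriptive and without significance tests:

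- participants with at least one Grade 3/4 event or serious adverse event;
- PHQ-9 Item 9 scored 1 or more at Week 12 and, separately, at Week 24, among those assessed, with exact 95% intervals and the number not assessed.

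Do not pool PHQ-9 results from BtB sessions into any between-arm count. Report positive Patient Suicidality Forms by arm only if they are captured in the study data. The protocol routes completed forms to the investigators and does not say that they are entered in the database.

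The cost is SAP wording and a few extra tables, with no new visits or assessments for the two summaries above. Two limitations should be stated with the results. The intervals are wide. Contact is also unequal, because BtB participants are seen or called weekly while UC has no formal contact before Week 12. This may inflate adverse-event reporting in BtB. Where detection at a session leads to treatment or withdrawal, it may also lower BtB ideation at Weeks 12 and 24. Both effects can be disclosed but not removed.

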9.12 Interim Analysis

No interim analysis will be performed.

9.13 Subgroup Analysis

Exploratory subgroup analysis will be performed based on sex, age (<50 vs. ≥50 years), and pharmaceutical antidepressants.

9.14 Missing Data

Multiple imputations will be adopted to account for missing data. If differential missing patterns are observed, sensitivity analyses will be performed to evaluate the consequences of potential missing mechanisms.

9.15 Data Management

A comprehensive web-based data management system will be developed for this study using REDCap by the IUCDCC which will allow controlled entry through the internet. REDCap provides a secure, web-based environment that provides an intuitive data entry interface and has real-time validation rules (with automated data type and range checks). The system offers easy data manipulation with logged auditing, functionality for reporting, monitoring and querying subject records. An experienced Database Administrator provides database creation, daily backup, and installation of security patches.

A unique identifier will be assigned to each study participant and their associated study specimens. Patient identifiers will be located only within the subject's study file in a separate, locked cabinet within the Infectious Diseases Research unit at the ICRC. Hardcopies of laboratory source records will also be stored in a locked file cabinet. All entryways to the IDRC are secured by padkey codes. Initial screening, consenting of potential subjects, and data abstraction and recording will be completed by either the primary investigators or by the research study coordinators from the IDRC.

The data management system will facilitate quality control efforts, prevent entry of erroneous values, provide warnings for possible outliers, generate missing data reports, track subjects and samples, and assist in the preparation of data for statistical analysis. All data will be reviewed and processed through multiple verification and edit checking programs post entry to ensure data quality.

10.0 HUMAN PARTICIPANTS RESEARCH AND PROTECTION

10.1 General Considerations/Investigator Training

The Human Participants Research outlined in this proposal meets the definition of a Phase II clinical trial for the purpose of identifying biological and physiological mechanisms of human disease (not for identifying the superiority of one agent over the other). Therefore, a formal Data and Safety Monitoring Board is not required, although appropriate monitoring through the Data and Safety Monitoring Plan with independent monitor as described below will be fully implemented. This trial will be posted on ClinicalTrials.gov and updated regularly as needed for protocol updates and results. All Indiana University personnel involved with this application have successfully completed the training and examination involved with the Collaborative Institutional Training Initiative Course.

10.2 Risks to the Participants

10.2.1 Human Participants Involvement and Characteristics

- A total of 110 HIV-infected participants will be recruited to participate in this pilot trial investigating the efficacy of cognitive behavioral therapy using the Beating the Blues computer program to reduce inflammation and improve endothelial function.
 - Participants must be at least 18 years of age, have documented HIV infection, have a screening HIV-1 RNA level <75 copies/mL while on ART for at least one year, and have a screening PHQ-9 score ≥ 10 .
 - The chief exclusion criteria include known CVD, congestive heart failure, treatment for malignancy (besides localized skin cancers) within 6 months of screening, uncontrolled diabetes (defined as screening Hgb A1c >8.0%) or newly diagnosed glucose intolerance (defined as screening glucose ≥ 140 mg/dL), uncontrolled hypertension (systolic BP >160 mmHg or diastolic BP >110 mmHg), screening eGFR <50mL/min/1.73² (using the 2009 CKD-EPI creatinine formula), screening total cholesterol >240 mg/dL, pro-inflammatory conditions besides HIV infection (e.g. autoimmune diseases, but allowing hepatitis B or C co-infection).
 - Potential participants will be recruited from the HIV outpatient clinics of Indiana University Health Hospitals and Eskenazi Health Hospital. All biologic/physiologic study procedures will occur in the Indiana Clinical Research Center at Indiana University Health University Hospital.

10.2.2 Sources of Materials

- All data for this study will be obtained only after written, informed consent is provided by each participant. Existing medical records will be reviewed for demographics, medical diagnoses, and medications. Blood samples will be obtained for testing of chemistries, cell counts, HIV-1 RNA levels, CD4 cell counts, inflammatory/coagulation markers, and metabolic markers. Urine samples will be obtained for pregnancy testing. Urine, serum, plasma, and DNA will be obtained for future studies of interest. Questionnaires to assess depression, medication adherence, tobacco use, physical activity, anxiety, anger/aggression, positive/negative effects, and sleep quality will also be implemented. Ultrasound images from the brachial artery flow-mediated dilation testing will also be collected.
- Results from pertinent medical records and procedures performed for these studies, as outlined above, will be recorded on the human participants involved in the projects in this application.
- Data will be stored in a password-protected computerized database via REDCap that will include only the participants' study identification number (names and other identifiable information will not be included). Therefore, the SID# will be the only link to the participant. Only the principal investigators, co-investigators, and research personnel who will directly obtain the necessary data will have access to the participant identities. All data obtained for this study will be obtained only after written, informed consent is provided by each participant.
- Records will be reviewed manually. Urine specimens will be obtained via standard clean-catch technique. Blood specimens will be obtained via peripheral venipuncture. Flow-mediated dilation of the brachial artery will be measured using high frequency ultrasound with images downloaded to a secure, encrypted electronic database. Beating the Blues treatments and questionnaires will be completed in private settings. These data will be collected solely for the purpose of the proposed research projects.

10.2.3 Potential Risks

- There are minimal risks to the participants enrolled in the proposed research. The first is the potential loss of participant confidentiality. The second consists of the risks associated with blood drawing/needle sticks, which include pain, bruising, infection, and phlebitis. The amounts of blood to be drawn at screening and at each main study visit are 15 cc (one tablespoon) and 60 cc (four tablespoons), respectively. The total amount of blood to be obtained over the 24 week study period would be approximately 255 mL (17 tablespoons), which is well within the accepted standards for blood donation over a 6 month period. The primary risks associated with nitroglycerin administration as part of the brachial artery testing are headache and transient hypotension. NTG may also infrequently cause the sensation of flushing of the skin and rash. There may also be moderate pain associated with the inflation of forearm cuff as part of the brachial reactivity testing. There are no known risks related to the implementation of the Beating the Blues cognitive behavioral therapy program. Participants may also feel unease in completing the questionnaires.
- The principal alternative to these procedures would be not to participate in the research.

10.3 Adequacy of Protection Against Risks

10.3.1 Recruitment and Informed Consent

- Recruitment will only begin once the Indiana University Institutional Review Board has approved this study. All participants will be recruited from the outpatient HIV care clinics at Indiana University Health Hospitals and Eskenazi Health Hospital. Self-referrals from other venues will also be considered. If the primary caregiver for the patient believes he or she is eligible for the study and allows the patient to be

approached for screening, one of the study investigators or a study nurse will approach each potential participant during his or her regularly scheduled clinic visit. If eligibility is confirmed, then the purpose, procedures, and risks and benefits of the study will be discussed with the participant. Participants will have ample opportunity to ask questions and to have all concerns addressed. If the participant wishes to pursue screening, then written informed consent will be obtained (and a copy given to the participant). All consent forms will be stored in a locked file cabinet.

